12.3.9 Procedures for Reporting

Serious adverse events, unexpected AEs, and unanticipated problems will be reported to the IRB, NIAMS Clinical Director, and DSMC according to the NIH-OHSRP SOP 16, "Reporting Requirements for Unanticipated Problems, Adverse Events and Protocol Deviations." All patients who receive at least one dose or part of a dose of the trial medication (pioglitazone), whether withdrawn prematurely or not, will be included in the safety analyses. All data relating to safety will be listed and summarized separately for the treatment period and for the entire study. All safety reports will be reviewed by the Principal Investigator.

12.3.10 Reporting Timeline:

Adverse events, protocol deviations, unanticipated problems (UP), Unanticipated Adverse Device Effects (UADEs), serious adverse events, sponsor and serious, are defined as described in NIH HRPP SOP 16 ("Reporting Requirements for Unanticipated Problems, Adverse Events and Protocol Deviations."). All adverse events occurring during the study, including those observed by or reported to the research team, will be recorded. Serious unanticipated problems and serious protocol deviations, will be reported to the IRB, DSMC and Clinical Director as soon as possible but not more than 7 days after the PI first learns of the event. Not serious unanticipated problems will be reported to the IRB, DSMC and Clinical Director as soon as possible but not more than 14 days after the PI first learns of the event. Not serious protocol

deviations will be reported to the IRB as soon as possible but not more than 14 days after the PI first learns of the event.

Deaths will be reported to the Clinical Director, DSMC and IRB within 7 days after the PI first learns of the event.

12.3.11 Reporting of Non-Serious Protocol Deviations:

Non-serious protocol deviations will only be reported to the IRB (within 14 days after the PI first learns of the event) if they represent a departure from NIH policies for the conduct of human subjects research, adversely affect the health care of the subject(s) or compromise the interpretation or integrity of the research. Non-serious protocol deviations that result from normal subject scheduling variations or technical issues associated with sampling that does not impact the health of the subject or the interpretation of the study data will not be reported.

12.3.12 Reporting of Adverse Events:

The PI is responsible for summarizing all serious adverse events and adverse events at least possibly related to the research procedure and interventions at the time of Continuing Review.

12.3.13 Reporting of Deaths:

All deaths that have occurred among study participants since the previous review will be summarized at the time of continuing review.

12.3.14 Reporting Waivers:

Waiver of Reporting to the IRB of anticipated minor protocol deviations, adverse events and deaths due to underlying disease or population under study unless determined to be an Unanticipated Problem.

- Non-unanticipated problems (UP)/ adverse events will not be reported to the IRB unless they occur at a rate greater than that known to occur in patients with SLE. If events are occurring substantially more frequent than would be anticipated in typically treated patients with SLE, they will also be reported to IRB. The following anticipated adverse events will not be reported to the IRB unless they occur at a severity greater than that known to occur in patients taking pioglitazone: lower extremity edema, decrease in Hb which is less than 1.5 g/dl, weight gain <5 pounds/week. Examples of expected adverse events include those events detailed in the Investigator's protocol for pioglitazone and

in the pioglitazone drug insert. No more than a total gain of 15% weight gain if associated with signs and symptoms of volume overload such as shortness of breath on exertion, paroxysmal nocturnal dyspnea or elevated jugular venous pressure will be allowed for the total duration of the study. If patient gained weight during study due to other reasons such as lifestyle changes or increase in Prednisone dose or other specific reasons and the patient is not at risk of health compromising condition, these reasons will be documented in CRIS and will not be reported as Unanticipated Problems. Patient will be advised to lose weight through NIH nutrition consults or exercising. If the rate of these events exceeds the rate specified in the protocol or investigator's brochure the events will be classified and reported as though they are Unanticipated Problems.

12.3.15 Adverse Event, Protocol deviation and Unanticipated Problem Assessment and Follow-up:

In the event of an adverse event, protocol deviation and unanticipated problem the first concern will be for the safety of the patients. Investigators are required to collect and document all adverse events (AEs), protocol deviations and unanticipated problems. At each study visit, the Principal Investigator will inquire about the occurrence of AE/SAEs since the last visit, and review any protocol deviations and unanticipated problems. Adverse events (including SAEs), protocol deviations, and unanticipated problems may be discovered through any of these methods:

- Observing the subject.
- Questioning the subject in an objective manner.
- Receiving an unsolicited complaint from the subject.
- Review of all source documentation related to study procedures; abnormal values or results from clinical or laboratory evaluations (including, but not limited to, radiographs, ultrasounds, or electrocardiograms) can also indicate adverse events.

Events will be followed for outcome information until they return to baseline or stabilize. Study-related AEs will be followed and/or treated at the NIH until resolution or stabilization of the AE, after which the subject will be referred to a physician(s) outside of the NIH for care and follow-up.

12.3.16 Adverse Event Recording:

Adverse events will be monitored throughout this study, and these events will be recorded on the appropriate AE eCRF at each visit after starting study medication. The record for each event will include the following information:

- Description of the event.
- Onset and stop dates of the event.
- Seriousness of event.
- Intensity (or severity) of the event.
- Action taken because of the event.
- Relationship of the event to study drug and/or study procedure.
- Outcome of the event.
- Expectedness of the event.

12.3.17 Pregnancy Reporting and Follow-up:

This study includes pregnancy information as safety data and pregnancies will be recorded if they begin any time after enrollment. Information about any pregnancy should be reported promptly to the NIH NIAMS/NIDDK IRB, NIAMS Clinical Director, and DSMC on the same timeline as a SAE. All pregnancies identified during the study must be followed to conclusion and the outcome of each must be reported. The investigator should be informed immediately of any pregnancy in a study subject or a partner of a study subject. A pregnant subject should be instructed to stop taking study medication. The investigator will refer patient to High-risk Obstetrics for counseling and follow-up. Pioglitazone has a pregnancy risk factor Category C; there are no adequate and well controlled studies in pregnant women. Animal studies show increased rates of post-implantation loss, delayed development, reduced fetal weights, and delayed parturition at doses 10 to 40 times the maximum recommended human dose (Label, 2013). Monitoring of the pregnant subject should continue until the conclusion of the pregnancy, and a follow-up Pregnancy Monitoring form detailing the outcome of the pregnancy should be submitted to the IRB. When possible, similar information should be obtained for a pregnancy occurring in a partner of a study subject. Information requested about the delivery will include:

- Subject's enrollment ID
- Gestational age at delivery

- Birth weight, length, and head circumference
- Gender
- Appearance, pulse, grimace, activity, and respiration (APGAR) score at 1 minute, 5 minutes, and 24 hours after birth, if available
- Any abnormalities.

Should the pregnancy result in a congenital abnormality or birth defect, an SAE also must be submitted to the NIH NIAMS/NIDDK IRB using the SAE reporting procedures described above.

12.3.18 Lost to follow up patient reporting:

After three attempts to contact the patient via phone, a certified letter will be sent to notify him or her that they have been withdrawn from the study.

12.3.19 Stopping Rules:

If any of the involved entities believes there is any evidence of a pattern of unanticipated AEs (regardless of causality) or SAEs an unscheduled independent third party review by the DSMC will be requested. Based on the conclusions of the review, the PI will either terminate the study or modify the protocol. Additional stopping rules may be set at any time by the IRB or DSMC. Due to the interventional nature of the protocol, we expect to work closely with an assigned DSMC.

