9.4 Screening and Randomization

Subjects will review and sign informed consent document, and medical history, physical exam, disease activity (SLEDAI-2K), screening labs and echocardiogram will be performed.

Echocardiogram will not be performed if patient is rescreened within 6 months and previous result is normal or if patient had normal Echocardiogram within 6 months prior to screening.

Routine laboratory data obtained within 30 days of the screening visit under the natural history protocol 94-AR-0066 can be used for screening. Screening labs will include infectious disease testing for HIV, Hepatitis B, Hepatitis C and Tuberculosis if they have not been obtained within the last 6 months. As mentioned above, postmenopausal women without a DEXA scan in the last year will undergo a DEXA scan to assess eligibility. The window between screening and baseline must be less than 46 days, otherwise subjects will need to be rescreened regarding labs. Inclusion/Exclusion Criteria will be signed off based on screening labs and assessment. Patients who meet these criteria will be randomized to a sequence of active drug followed by placebo, or placebo followed by active drug in a 1:1 allocation ratio. Randomization and drug/placebo allocation will be done by the NIH clinical center research pharmacy after screening visit.

We will test Urinalysis (includes microscopic) on Screening and Month 8 visits on all patients. If patients have evidence of microscopic hematuria > 20 RBCs/uL(excluding normal menstruation cycle) it will be repeated twice at one month (+/- 7 days) intervals and if RBCs

are consistently more than 20 RBCs/uL then Urology consult will be placed. The following algorithm will be put in place, per recommendations by the Urology service at NCI:

1. Question patient about macroscopic hematuria > 20 RBCs/uL times 3 results.
 - a. If YES → Urology consult → Cytology
 - i. If abnormal cytology → Cystoscopy → FISH @ Mayo Labs for genetic changes for bladder cancer detection
 - ii. If normal cytology → Nothing

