9.5 Study Visits

9.5.1 *Baseline visit and 5-month +/- 7 days (post-washout) visit*

- a. Baseline visit will include medical history. The baseline and 5-month (post-washout) visits will consist of a physical exam, and blood draw for biomarkers (Table 3). SF-36, PGA, disease activity (BILAG 2004, SLEDAI-2K) and vascular measurements will be determined and subjects will be issued a 3-month supply of blinded study drug or placebo with instructions. The first week of each treatment arm, patients will take two 15 mg capsules of pioglitazone daily (30 mg total daily dose) and, if no significant side effects develop (primarily fluid retention), will increase to three 15 mg capsules (45 mg total daily dose). Subjects will be instructed to follow the same titration for the placebo arm. Patients will be called prior to increasing the dose to 45 mg to question patients about rapid weight gain (>5 pounds in a week), significant edema or other side effects. Patients will be called 1-2 weeks after increasing dose to 45 mg daily to assess tolerability. If 45 mg dose is not well tolerated but the 30 mg dose is well tolerated, dose will be decreased back to 30 mg daily for duration of trial. PET/CT exams will be performed in 15 patients initially randomized to placebo and 15 patients initially randomized to pioglitazone and the investigators will be blinded to this. PET/CT studies will only be performed at baseline and month 3. Subjects can opt out of the PET/CT scan and still participate in the study. Patients will be asked to participate at baseline until we reach 15 patients/group. If a patient is found to have an acute infection at the baseline visit, they will be given antibiotics and their next visit will be scheduled for no more than 4 weeks later, at which time they will start the study medication. We will repeat only baseline clinical labs at this extra visit; we will not repeat PET/CT, vascular function studies or research sample collection. If a patient has an abnormal lab result at the baseline visit that requires a repeat, the patients next visit will be scheduled no more than 4 weeks later, at which time if the abnormal lab has improved or normalized they will

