10.2 Study Completion Criteria

A subject is considered to have completed the study when he/she has completed 8 months in the trial and received both treatment arms of the study. Enrolled subjects who withdraw from the trial prior to receiving study agent or who only complete one arm will be replaced; however, patients who complete only one arm will still be included in analysis.

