10.4 Blinding, Packaging, Labeling and Storage

Study agent (15 mg pioglitazone or placebo) will be packaged in identical vials each containing 300 capsules. Both study agents will be blinded using identical-looking capsules prepared by a vetted vendor selected by the NIH Pharmaceutical Development Service (PDS). Each vial will be labeled with a treatment number specific to the subject. A 300 capsule (one vial) supply of study agent will be given to each subject at enrollment at the baseline visit and at month 5. The amount of study agent dispensed will be sufficient to last from baseline to month 3, and from month 5 to month 8. The randomization code will be provided by the Clinical Center Research Pharmacy, as mentioned above. Emergency unblinding will occur in the case of a serious adverse event (SAE) that is considered potentially secondary to the drug. Unblinding will be performed by PDS. Only the pharmacists will be unblinded throughout the trial. The subjects, the investigators, and the study site staff will remain blinded to study medication assignment during the entire study period. Compliance with study treatment and pill counts will be performed by the research nurse/study coordinator and this information will be provided to PDS as well.

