12 HUMAN SUBJECT PROTECTION ISSUES

12.1 Selection

12.1.1 *Human Participants Involvement and Characteristics*

For the purposes of this study, human participants will undergo physical examination and questionnaire completion, CAVI, Endopat, FDG PET CT and DXA scan (a subset of subjects), blood draws, Echocardiogram, and exposure to study drug (pioglitazone and placebo). There will be no involvement of fetuses, neonates, children, pregnant women, prisoners, or institutionalized individuals. Women of childbearing potential will be included, but risk reduction measures (including required contraception and pregnancy testing) are in place to protect them.

12.1.2 *Inclusion of Women, Minorities, and Children:*

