12.2.2.6 Study Drug

Participants will be randomized to pioglitazone or placebo and all patients will at some point receive pioglitazone given the crossover nature of trial. Risks of pioglitazone use in this population (i.e. non-diabetic) are as follows:

- Decreases in hemoglobin and hematocrit of 2-4%. These reductions may be due to an increase in plasma volume and usually pose only minor risk. CBC will be monitored on all patients at each study visit.
- Mild to moderate edema. Pioglitazone is contraindicated in patients with NYHA Class III or IV cardiac failure. In diabetics, concern over the use of rosiglitazone and worsening CV outcomes is still a matter of debate but a black box has been included in the medication guide describing a risk for congestive heart failure exacerbation in individuals taking TZDs. For our study, all patients will undergo a baseline echocardiogram and will be excluded for an ejection fraction <45% and/or evidence of NYHA class II-IV.
- Hepatic effects. Pioglitazone can cause decreases in hemoglobin and hematocrit of 2-4%. These reductions may be due to an increase in plasma volume and usually pose only minor risk. While pioglitazone is typically not associated with hepatic toxicity or liver function test (LFT) elevations, the pioglitazone package insert states there are post marketing reports of hepatic failure and that causality cannot be excluded; Medwatch report states there is an association with hepatitis, hepatic enzyme elevations to 3 or more times the upper limit of normal. Pioglitazone is structurally related to troglitazone

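### The safety set requires a dose of pioglitazone, so read literally it omits placebo-first patients who leave before month 5 but keeps their pioglitazone-first counterparts

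*Combined protocol and SAP*

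**What the plan says.** Section 12.3.9 contains the only statement of who enters the safety analyses: "All patients who receive at least one dose or part of a dose of the trial medication (pioglitazone), whether withdrawn prematurely or not". The next sentence says that safety data will be listed and summarised for the treatment period and for the whole study, but it names no population. Section 11 plans an intent-to-treat primary analysis and does not define a safety set.

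The design that this rule has to serve is set out elsewhere:

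- Section 9.4: patients are "randomized to a sequence of active drug followed by placebo, or placebo followed by active drug in a 1:1 allocation ratio".
- Section 10.4: a one-vial "supply of study agent will be given to each subject at enrollment at the baseline visit and at month 5". Section 9.5.3 confirms that nothing is dispensed at months 3 and 8.
- Section 8: each treatment period lasts three months, with an 8-week washout between them.

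Terms for the product are not used consistently. Section 10.4 counts placebo as study agent ("Study agent (15 mg pioglitazone or placebo) will be packaged in identical vials"), and section 12.1.1 likewise counts placebo as study drug. Section 9.5.1 sets the two against each other: "subjects will be issued a 3-month supply of blinded study drug or placebo with instructions".

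Two other statements bear on the point. Section 12.2.2.6 says "all patients will at some point receive pioglitazone given the crossover nature of trial". Section 10.2 says "patients who complete only one arm will still be included in analysis".

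**The concern.** In a crossover trial every dosed patient normally belongs in the safety set, and events are attributed to the agent being taken. Here the parenthesis in section 12.3.9 makes exposure to pioglitazone the condition for entry. Pioglitazone-first patients meet it with their first capsule. Placebo-first patients cannot meet it until month 5, after three months of placebo and the washout.

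The rule therefore treats patients who leave at the same time differently according to their randomised sequence, and every patient it omits has taken placebo only. Two analysts working from this document could build different safety sets, one reading the sentence literally and the other reading it as any study agent.

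These patients may well have events to report. The discontinuation criteria in section 10.1 include flares that do not respond to treatment, certain Grade 4 events and confirmed liver enzyme elevation. Under blinding, any of these can end participation during a placebo period.

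**Working it through.** The documents give no size for the safety set, so there is no figure to reproduce. The check has two parts: whether the asymmetry follows from the text, and how large it could be.

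**Does it follow from the text?** Take two patients who leave at the same time, after first dosing and before month-5 dosing.

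| Sequence | Agent taken | Meets the section 12.3.9 wording? |
|---|---|---|
| Pioglitazone first | Pioglitazone | Yes |
| Placebo first | Placebo | No |

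The other sections do not clearly change the second row:

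- Section 10.2 keeps patients who complete a single arm, but it does not say that this includes safety. It also does not cover someone who leaves partway through the first arm.
- Section 12.2.2.6 assumes that everyone eventually takes pioglitazone. That is untrue of exactly these patients.
- The varying use of study agent and study drug in sections 9.5.1, 10.4 and 12.1.1 does not settle what trial medication means, and the parenthesis picks the narrower meaning.

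**How large could it be?** Let N be the number dosed in each sequence and k the number leaving each sequence before month-5 dosing. Both are assumptions, as are equal numbers of leavers in the two sequences and month-5 dosing of everyone who remains. N cannot exceed 50, because the 100 patients in section 8 include screen failures. The documents do not give the timing of dropout. Section 11.1 gives its rate both as 3-20% and as 20% or more, so there is no ceiling for k.

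- Placebo-exposed, all dosed patients: N + (N − k) = 2N − k
- Placebo-exposed, literal rule: 2(N − k) = 2N − 2k
- Pioglitazone-exposed, either rule: N + (N − k) = 2N − k
- Share of placebo-exposed lost: k/(2N − k)

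| N | k | Placebo-exposed, all dosed | Placebo-exposed, literal rule | Share lost | Pioglitazone-exposed kept |
|---|---|---|---|---|---|
| 50 | 2 | 98 | 96 | 2/98 = 2.0% | 98 of 98 |
| 50 | 5 | 95 | 90 | 5/95 = 5.3% | 95 of 95 |
| 40 | 2 | 78 | 76 | 2/78 = 2.6% | 78 of 78 |
| 40 | 5 | 75 | 70 | 5/75 = 6.7% | 75 of 75 |

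If the whole of the projected 20% dropout fell before month 5, then with N = 50, k = 10 and the loss would be 10/90 = 11.1%.

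**Effect on the placebo event rate.** Let p be the adverse event rate among all placebo-exposed patients and s the rate among the omitted leavers.

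- Rate under the literal rule: [(2N − k)p − ks]/(2N − 2k)
- Change from p: k(p − s)/(2N − 2k)

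The rate falls if s > p, is unchanged if s = p, and rises if s < p. With N = 50 and k = 5 the multiplier is 5/90 = 0.056. If leavers' rate were 20 percentage points above p (an assumption), the placebo rate would be understated by 0.056 × 20 = 1.1 points. The documents give no value for s.

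**The case against.** The strongest reply is that the sentence says who is included and does not say that only they are. It also expressly keeps patients who withdrew early, and section 12.2.2.6 shows that the authors believed everyone would receive pioglitazone. On this view the parenthesis is just the product name. Section 10.2 points the same way for patients who finish a placebo arm and leave during washout, so the clear gap may be confined to those who leave within the first three months. In addition, all adverse events are recorded (sections 12.3.10 and 12.3.15), and the monitoring committee reviews accumulated events and unblinded data (sections 11.2 and 12.5). The plan specifies no pioglitazone-versus-placebo comparison of event rates.

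Much of this stands. The wording is probably loose drafting, the omission is one of analysis and not of data capture, and the practical effect is on descriptive summaries. It is also fair that the denominators above presuppose tabulation by agent received, which the plan does not state. In a whole-study summary, the total would shrink instead, for example from 100 to 95 with N = 50 and k = 5.

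The reply does not supply a sentence that admits placebo-only patients to the safety analyses. Section 10.2 does not mention safety, and the belief expressed in section 12.2.2.6 fails for the patients in question. Where the only stated rule names pioglitazone, intent should not have to be inferred.

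**Conclusion.** The concern holds and should be fixed. Followed as written, section 12.3.9 builds a safety set whose membership depends on randomised sequence for patients who leave before month-5 dosing. In the four cases tabulated, 2.0% to 6.7% of placebo-exposed patients are lost, against none of the pioglitazone-exposed. Those figures rest on assumed values of N and k, and no direction of bias is claimed. Confidence is high about the wording. The effect on results is likely to be modest and cannot be estimated from the documents.

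**What to change.** In section 12.3.9, replace the condition with one based on study agent: the safety population comprises every patient who took at least one full or partial dose of study agent, whether pioglitazone or placebo, regardless of early withdrawal. Add a sentence stating that events are summarised by the agent received, with the patients exposed to that agent as the denominator. The second sentence is needed because, in a crossover, the population alone does not determine the denominator for each agent.

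The cost is one corrected and one added sentence, best made before database lock. No new data, visits or procedures are needed, because all adverse events are already recorded.
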